4.0 Project Information

4.1 * What department(s) will be associated with this protocol?

Orthopedics

4.2 * Is the IRB of record for this study an IRB/HRPP that does NOT use EIRB? If Yes, complete the application according to the IRB/HRPP Determination.

If your Projects or Protocols are under the oversight of another IRB that does use EIRB, stop this submission and contact the core site and request an invitation as a performing site.

If your Project or Protocol is now being submitted for the first time to an IRB that does use EIRB, continue with this application and answer the questions to be reviewed by the IRB.

Answering yes means the board of record is an IRB that does NOT use EIRB.

Yes No

4.3 * Is this protocol research, expanded access, or humanitarian use device?

Yes No

4.4 * What type of protocol is this?

- Behavioral Research
- Biomedical Research
- Clinical trial (FDA regulated)
- Educational Research
- Expanded Access
- Humanitarian Use Device (HUD)
- Psychosocial Research
- Oral History
- Other

4.5 Are you conducting this project in pursuit of a personal degree?

Yes No

4.7 * Is this human subjects research? (As defined by 32 CFR 219) Human subject means a living individual about whom an investigator (whether professional or student) conducting research:

(i) Obtains information or biospecimens through intervention or interaction with the individual, and uses, studies, or analyzes the information or biospecimens; or
(ii) Obtains, uses, studies, analyzes or generates identifiable private information or identifiable biospecimens.

Yes No

4.8 * Do you believe this human subjects research is exempt from IRB review?

Yes No

5.0 Personnel Details**5.1 Does the Principal Investigator have a Permanent Change of Station (PCS) Date or Estimated Institutional Departure Date (EIDD)?**

Yes No

5.2 List any Research Team members without EIRB access that are not previously entered in the protocol:

No results found

5.3 Are any Contractors or Subcontractors involved in this study? If yes, please list them and describe their role.

Yes No

No results found

5.4

Will you have a Research Monitor for this study?

Yes
 No
 N/A

6.0 Data/Specimens

6.1 Does the study involve the use of existing data or specimens only (no interaction with human subjects)?

Yes No

7.0 Funding and Disclosures

7.1 Source of Funding:

Funding Source	Funding Type	Amount
No results found		

Total amount of funding:

0

7.2 Do you or any other Investigator(s) have a disclosure of a personal interest or financial nature significant with sponsor(s), product(s), instrument(s) and/or company(ies) involved in this study?

Yes No

All personnel engaged in research must complete and attach a Conflict of Interest (COI) form.

8.0 Study Locations

8.1 Is this a collaborative or multi-site study? (e.g., are there any other institutions involved?)

Yes No

8.2 Study Facilities and Locations:

Institution	Site Name	Site Role	FWA or DoD Assurance Number	Assurance Expiration Date	Is there an agreement?	IRB Reviewing for Site
No results found						

Other:

Other Institution Site	Site Role	FWA or DoD Assurance Number	FWA or DoD Expiration Date	Is there an agreement?	IRB Reviewing for Site
No results found					

8.3 Are there international sites?

Attach international approval documents, if applicable, when prompted. Note: Ensure local research context has been considered

Yes No

8.4 Is this an OCONUS (Outside Continental United States) study?

Yes No

Select the area of responsibility:

Have you obtained permission from that area of responsibility? (This is a requirement prior to study approval)

Yes No

9.0 Study Details

9.1 Key Words:

Provide up to 5 key words that identify the broad topic(s) of your study

Trigger point injections AND pain

9.2 Background and Significance:

Include a literature review that describes in detail the rationale for conducting the study. Include descriptions of any preliminary studies and findings that led to the development of the protocol. The background section should clearly support the choice of study variables and explain the basis for the research questions and/or study hypotheses. This section establishes the relevance of the study and explains the applicability of its findings

Opioid addiction and abuse have become a significant burden on the healthcare system since this class of medication was first used in the 1990s. Opioid medication's highly addicting properties have led to its classification as an epidemic by the CDC in 2011. Alternative means of pain control for highly invasive procedures need to be explored. Orthopedic surgery specifically accounts for an estimated 8.8% of iatrogenic opioid use disorder (Trasolini et al. 2018). More effort should be directed to explore non-opioid interventions in the post-operative setting of orthopedic surgery to reduce the use of opioids and risk of addiction.

In an orthopedic setting one of the most preformed surgeries is the total knee arthroplasty (TKA). This procedure is most commonly performed in cases of severe osteoarthritis; some other indications include rheumatoid arthritis, deformity, and trauma. There are several surgical techniques to achieve this operation; however, all include performing an arthrotomy which is creating a semi-permanent opening by dissecting the superficial soft tissue to expose the bony anatomy of the knee joint. Those bony structures include the distal aspect of the femur, the patella, and the superior aspect of the tibia. By performing the arthrotomy the surrounding muscles and fascia are manipulated and temporarily displaced leading to stiffness, trigger points, and pain. This constellation of symptoms makes up a condition called myofascial pain syndrome. Treatment of m

myofascial pain syndrome with use of trigger point injections has shown that inactivation of myofascial pain trigger points around the knee joint can promote structural remodeling of the surrounding skeletal muscle to regulate the biomechanical balance, thus improving the clinical symptoms of knee osteoarthritis (Lin et al, 2022).

There have been limited studies aimed at the treatment of myofascial pain syndrome in the acute setting of a TKA. Mayoral et al. (2013) conducted a randomized double-blinded, placebo-controlled clinical trial where patients who underwent a TKA had dry needling completed in the pre-operative and intra-operative setting. This study demonstrated an improvement in pain scores within the first month of surgery in the dry needling group compared to a sham group. This has been the only study to date to address direct intervention for myofascial pain syndrome around the operative time frame. Henry et al. (2012) conducted a prospective study in which patients on the waitlist for a TKA were treated with trigger point injections; patients reported an improvement in pain up until the TKA procedure could be completed. Although Henry et al. did not assess pain in the post-operative setting, this study nonetheless demonstrated that myofascial pain syndrome is a component of osteoarthritis.

Despite these favorable results there are no studies that look at trigger point injections in the post-surgical setting. The aim of this study is to perform trigger point injections with administration of a local anesthetic immediately following TKA to assess the effect on pain scores. The trigger point injection/experimental group will be compared to a sham injections/control group where a superficial injection will be made into the dermis and no anesthetic will be injected. Injections will include two injections to four muscle bellies: the vastus medialis, vastus lateralis, medial, and lateral gastrocnemius muscle belly. Injections will include 0.5 mL of lidocaine without epinephrine and will be outside of the operative area distal and proximal to the joint, the popliteal fossa and incision site. With each injection the plunger will be pulled back to ensure placement of the needle is outside vascular structures. To assess the primary outcome measures, patients will complete a Visual Analogue Scale (VAS) which ranges from 0 (no pain) to 100 (severe intolerable pain) on post operative day (POD) 1 and at follow-up visits during weeks 2 and 6. The secondary outcome will assess how much opioid medication (ie, MME) was used in the immediate post-operative period through the week 6 follow-up visit.

9.3

Objectives/Specific Aims/Research Questions:

Describe the purpose and objective(s) of the study, specific aims, and/or research questions /hypotheses

The aim is of this study is to explore the effect of a pain intervention (ie, trigger point injection) vs. a sham injection on managing post-surgical pain and reducing the reliance on systemic opioid analgesics. Outcomes include the VAS on POD1 and week 2 and week 6 follow-up appointments. Opioid use will also be evaluated during these intervals.

9.4 Study Design:

Describe study design in one to two sentences (e.g., prospective, use of existing records/data /specimens, observational, cross-sectional, interventional, randomized, placebo-controlled, cohort, etc.). Specify the phase – Phase I, II, III, or IV – for FDA-regulated investigational drug research

Prospective, interventional study comparing trigger point injections vs. sham injections on VAS pain scale ratings and opioid use.

9.5 Target Population:

Describe the population to whom the study findings will be generalized

DoD beneficiaries aged 45 years and older who will be receiving a TKA, on either knee.

9.6 Benefit to the DoD:

State how this study will impact or be of benefit to the Department of Defense

The purpose of this study is to explore a unique pain management modality to reduce the use of opioids following a routine surgery in the military hospital setting. This will benefit the Department of Defense by improving post surgical pain, decreasing overall opioid use which in turn may lead to decrease rate of opioid use disorders, shorter inpatient stays and decrease adverse medication side effects.

10.0

Study Procedures, Data Management, and Privacy

10.1 Study Procedures:

Describe step-by-step how the study will be conducted from beginning to end

Step 1: A HIPAA Waiver will be used to access MHS Genesis to obtain all joint surgeons' case lists for those patients scheduled for surgery, all those not scheduled for a TKA will be removed from the list. The principal investigator will review case lists to identify name, TKA procedure, date scheduled for TKA, and phone. Patients scheduled for a TKA will be contacted within two weeks of their surgery to discuss the study. Study inclusion and exclusion criteria will be reviewed with patients who are interested in participation to ensure they are eligible. Those who are eligible will be scheduled for an appointment with the principal investigator before TKA surgery, ideally at their pre-op visit (standard of care visit) but may occur on the day of their surgery, to review consent documents and answer any questions. In order to ensure patient understanding, a copy of the consent documents will be emailed (if email address is provided) to the patient prior to the appointment to allow him/her to review the consent in advance.

Step 2: Patients return for their appointment to review and sign the consent documents either at their pre-operative visit or day of surgery. Consents will be signed either during their pre-operative appointment in a clinic exam room or during the day of their surgery in the PACU. Consenting a patient in the PACU on the day of surgery is a last resort and all efforts will be made to complete consents during pre-operative clinic visit. During the consent phase the PI and/or AI will not be in military uniform and will not have their rank displayed. After consent documents are signed, participants are assigned to a study group. Due to academic time constraints (i.e. deadlines to complete and present the research), an alternating convenience sample approach will be taken for study group assignment. Each participant will be assigned a subject ID number based on their order of enrollment (e.g., the first participant enrolled will be assigned 1, second participant enrolled assigned 2, and so on). Every participant with an odd number will be placed in the trigger point injection group (experimental) and those assigned an even number will be placed in the sham injection group (control). Those in the trigger point injection group will have an E after the number and

those in the sham injection group an S. The study participants will not know which study group they will be assigned to. An equal number of participants will be included in each group (ie, trigger point injection vs. sham injection).

Step 3a: (Trigger point injection group) The principal investigator will identify relevant structures to include the vastus medialis, vastus lateralis, medial, and lateral gastrocnemius muscle bellies by utilizing anatomical landmarks. Once those structures are identified, each area will be prepped in an aseptic fashion with alcohol swabs. Two injections will be made in each muscle belly. Each injection will include 0.5 mL of 1% lidocaine without epinephrine. A total of eight injections will be administered with a total of 4 mLs of 1% lidocaine without epinephrine using a 1 ½" 25-gauge needle. A separate needle and syringe will be utilized for each of the four muscle bellies. Careful consideration to avoid neurovascular structures will be taken by retracting the plunger to ensure needle placement is outside vascular structures with each injection. A blind will be placed between the patient and the needle in order for the patient not to witness the injection, which is the same protocol as the sham injection. The blind used will be a drape or other soft item held by a person not involved with the study to obscure the vision of the subject during the injection and allow the investigator to use both hands to safely conduct the injection and aspiration procedure. The local anesthetic will be massaged into the area to ensure the medication disperses thoroughly into the muscle belly. After the needle is removed, the area will be cleaned with alcohol swabs and a bandage will be applied. This will be completed on POD 0 (ie, the day of the TKA procedure). Within the informed consent the consenting verbiage will ensure that the participants will not be able to identify injection technique that will identify whether they are in the sham or experimental group.

Step 3b: (Sham injection group) The principal investigator will identify relevant structures to include the vastus medialis, vastus lateralis, medial and lateral gastrocnemius muscle. Once those structures are identified using anatomical landmarks, each area will be prepped in an aseptic fashion with alcohol swabs. A needle with a syringe filled with sterile water will be inserted into the epidermis to mimic an actual trigger point injection. The needle will be left in place for 3-5 seconds to create the false perception of injection anesthetic into the muscle groups. No sterile water will be injected into the participant. Since the effects from the anesthetic block will still be active and the injections will be administered in a position that prevents the participant from viewing the procedure, participants will not know that there is nothing being injected into the area. This will occur by placing a blind between the patient and the needle in order for the participant not to see that no water will be injected. The blind used will be a drape or other soft item held by a person not involved with the study to obscure the vision of the subject during the sham injection and allow the investigator to use both hands to safely conduct the sham injection procedure. After the needle is removed the area will be cleaned with alcohol swabs and a bandage will be applied. Four separate needles and syringes will be utilized for each location. This will be completed on POD 0 (ie the day of the TKA procedure). Within the informed consent the consenting verbiage will ensure that the participants will not be able to identify injection technique that will identify whether they are in the sham or experimental group.

Step 4: On POD0 (after TKA surgery, the investigator will review MHS Genesis to obtain demographic information (age, sex, beneficiary status, BMI), morphine milligrams equivalents (MME) using the Medication Administration Record (MAR) Summary, prior pain medication history, diabetic history, tobacco use, anesthetic block type, surgical site, ICD codes, complications, and discharge disposition.

Step 5: On POD1, participants in each study group will be provided with the VAS and Opioid Use questionnaires. The VAS pain scale questionnaire will be used to report average pain scores by placing a hash mark (/) on the numbered scale

on the region that best represents their pain and writing the number (a whole number) on the form; scores range from 0 (no pain) to 100 (severe intolerable pain). The Opioid Use questionnaire will be used to document average opioid use following discharge. Both questionnaires will be completed by all participants at POD1, week 2 and week 6 visits. The VAS will be given to the participant with the intake form that is provided by the orthopedic technician, and the investigator will provide the Opioid Use questionnaire to the participant during the visit, and review the MAR Summary to obtain and calculate the total MME from POD0 to POD1 using MDCalc . Prior to ending the visit, the investigator will ask participants to bring in their opioids to be physically counted at their week 2 and week 6 visits.

Step 6: The investigator will provide a reminder phone call 1-2 days prior to the week 2 and week 6 appointments to ensure participants remember to bring in their medication.

Step 7: Participants return for the week 2 and week 6 visits. They are given VAS and Opioid Use questionnaires to complete, and opioid medication is counted. Once opioids have been accounted for, MME will be calculated.

10.2 Data Collection:

Describe all the data variables, information to be collected, the source of the data, and how the data will be operationally measured.

Injection type: Dichotomous variable. Trigger point or sham injection.

Visual analogue scale: Discrete variable. Will be scaled from 0 (no pain) to 100 (severe intolerable pain) and will be measured at POD1, week 2, and week 6. The VAS will be presented to the participant on paper.

Morphine milligram equivalent (MME): Discrete variable. Will be measured from POD 0 to POD1, then a total MME will be calculated from POD1 to week 2 and week 2 to week 6. This will be calculated utilizing the MME calculator on MDCalc.

Block: Categorical variable. Spinal, adductor or femoral nerve block determined by anesthesiology.

Age: Continuous variable. Age stated in years at time of surgery as stated in EHR.

Prior Pain Medications: Categorical variable. Obtained from EHR.

Discharge disposition: Dichotomous variable. Discharge to skilled nursing facility or home, discharge disposition will be reviewed in the discharge summary.

Active Duty, Dependent, Retiree: Categorical Variable.

Sex: Categorical (male, female). Obtained from EHR.

BMI: Categorical variable. Obtained from EHR. Categories will be BMI of 24.9 or less, BMI 25-29.9, and BMI greater than or equal to 30.

Nicotine use: Dichotomous variable. Obtained from EHR. Current use at time of injury.

History of Diabetes: Dichotomous variable. Obtained from EHR.

ICD Code: Categorical Variable. Obtained from EHR.

Laterality: Categorical Variable. Left or Right TKA

Complications: Categorical Variable. Pulmonary embolism/deep vein thrombosis, surgical site infection, severe pain from the injections, other, and multiple for more than one complication.

10.3 At any point in the study, will you request, use, or access health information in any form, including verbal, hard copy and electronic?

Yes No

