Patients will be recruited through use of a HIPAA Waiver to access joint surgeon case lists. Patients scheduled for a TKA will be contacted by the principal investigator and informed of the study. Those who desire to participate will have study inclusion/exclusion criteria reviewed to determine eligibility. Those eligible will be scheduled a consent appointment. The investigator will offer to email (or provide by hard copy) consent document to review prior to the appointment. When patients return for consenting, they will be taken to a private room (clinic exam room or private room in the PACU) to conduct the consent procedures. Consent documents will be reviewed with patients and any questions asked will be answered. Patients who desire to enroll in the study will sign the consent documents. The investigator will sign the consent documents, then provide a copy to the patient. During the recruitment and consenting phase, the PI or AI will not be in military uniform or have their rank visible.

13.5 DoDI 3216.02 requires an ombudsman to be present during recruitment briefings when research involves greater than minimal risk and recruitment of Service members occurs in a group setting. If applicable, you may nominate an individual to serve as the ombudsman.

N/A
 Propose ombudsman

13.6 Withdrawal from Study Participation:

Explain the process for withdrawal and specify whether or not the subjects will be given the opportunity to withdraw their data or specimens in the event they wish to withdraw from the study

At any point in the study participants can self-withdrawal from the study if they have a poor response to the injections, are unable to tolerate all injections, not willing to complete questionnaires, intraoperative complications (pulmonary embolism, deep vein thrombosis, surgical site infection, multiple or other), not willing to bring in their medications or if they choose to no longer participate in the study. However, any data collected prior to withdrawal will still be analyzed.

14.0

Risks and Benefits

14.1

Risks of Harm:

Identify all research-related risks of harm to which the subject will be exposed for each research procedure or intervention as a result of participation in this study. Consider the risks of breach of confidentiality, psychological, legal, social, and economic risks as well as physical risks. Do not describe risks from standard care procedures; only describe risks from procedures done for research purposes

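### The arm is fixed at consent although the arms differ only in an injection after surgery, so pre-injection losses and block choice fall after assignment when they need not

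*Combined protocol and SAP*

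**What the plan says.** - **Time of assignment (10.1, Step 2).** "After consent documents are signed, participants are assigned to a study group". Odd enrollment numbers go to trigger point injection and even numbers to sham, and the ID then carries an E or an S.
- **Time of consent (10.1, Steps 1 and 2).** "Patients scheduled for a TKA will be contacted within two weeks of their surgery to discuss the study", and "all efforts will be made to complete consents during pre-operative clinic visit". There is an exception: "Consenting a patient in the PACU on the day of surgery is a last resort". Section 13.4 also mentions a private PACU room, whereas section 13.1 rules out consent on the day of surgery.
- **Time of treatment (9.2; 10.1, Step 3a).** The injection follows the operation: "This will be completed on POD 0 (ie, the day of the TKA procedure". Step 3b gives the same day for the sham.
- **Block (10.2).** "Spinal, adductor or femoral nerve block determined by anesthesiology". Section 11.1 tests it between arms together with age, sex and history, and adjusts or stratifies if the difference is significant.
- **Withdrawal (13.6).** Listed reasons include "intraoperative complications (pulmonary embolism, deep vein thrombosis, surgical site infection, multiple or other").
- **Group sizes (10.1, Step 2).** "An equal number of participants will be included in each group (ie, trigger point injection vs. sham injection").
- **Masking (10.1, Step 2).** Participants are not told their arm. Nothing is said about investigators, surgeons or anesthesiology.

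**The concern.** Assignment is best placed as close as possible to the point where the treatments diverge. Whatever happens between the two is post-assignment: it can no longer be treated as baseline, and patients who leave in that interval leave from an arm.

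Here the interval contains the anesthetic block, the operation and any cancellation or early withdrawal. The first VAS is on POD1 and there is no earlier one, so a patient who is cancelled or withdraws before injection contributes nothing to the primary outcome but has already consumed a number. The plan names no analysis population and has no rule for patients assigned but never injected. With 10-15 per arm, a few such patients matter. The arm is also known throughout the interval to the investigator who will inject, so decisions about who goes on to injection are not protected from that knowledge.

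**Working it through.** **1. Order of events**

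| Event | Preferred route (consent at pre-op visit) | Last-resort route (consent in PACU) |
|---|---|---|
| Arm fixed | At consent, before surgery | At consent, on day of surgery |
| Cancellation, early withdrawal | After assignment | Mostly before assignment |
| Block and surgery | After assignment | Possibly before assignment |
| Injection | POD 0, after surgery | POD 0, after surgery |

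Section 20.2 defines PACU as the post-anesthesia care unit, so the second route may put assignment after surgery; yet Step 1 places the appointment before surgery. If section 13.1 governs, every patient follows the first route. The interval runs from 0 to about 14 days. The upper end is inferred from the contact window; no consent-to-surgery interval is stated.

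**2. The plan's sample size reproduces**

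Inputs from 11.5: two-sided alpha 0.05, power 0.80, Wilcoxon Mann Whitney test. Method: noncentral t power with each n multiplied by 3/π, the efficiency of the rank test for normal data.

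- Effect 1.1, 15 per arm: power 0.81.
- Effect 1.4, 10 per arm: power 0.82.

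The stated sample sizes stand. This point does not change them.

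**3. Illustration of pre-injection loss**

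The documents give no pre-injection loss rate. Assume 10% of 30 consented patients, range 5-15%: 30 × 0.05 = 1.5, 30 × 0.10 = 3, 30 × 0.15 = 4.5, or about 2 to 5 patients. Using the plan's difference of 28 and SD of 25 (28/25 = 1.12) and the method of step 2:

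| Lost before injection | Arms left | Power |
|---|---|---|
| 0 | 15 / 15 | 0.82 |
| 2 | 14 / 14 or 15 / 13 | 0.79 |
| 3 | 14 / 13 | 0.78 |
| 3 | 15 / 12 | 0.77 |
| 5 | 13 / 12 | 0.74 |
| 5 | 15 / 10 | 0.73 |

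If 3 of 30 are lost at random, the chance that all come from one arm is 2 × C(15,3)/C(30,3) = 2 × 455/4060 = 22%. The imbalance itself costs little (0.78 against 0.77); most of the loss of power comes from the smaller total. Issuing numbers alternately only to patients about to be injected would keep the injected arms within one patient of each other, however many were lost earlier.

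**4. Block type as a baseline variable**

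Section 11.1 adjusts for block only if the arms differ significantly. Suppose, purely for illustration, two block categories truly split 40% against 60% between arms. The chance that the test flags it is:

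| Per arm | Chi-square | Fisher |
|---|---|---|
| 15 | 18% | 10% |
| 10 | 13% | 5% |

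So the planned check would usually miss a moderate imbalance. This shows that the safeguard is weak; it does not show that such a split will occur.

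**The case against.** **No route to the clinical team is documented.** A reader might infer that surgeons or anesthesiology will choose analgesia knowing the arm. The documents do not support that. Block is anesthesiology's decision, no passage gives them the arm, and sections 14.2 and 14.3 restrict the data set to investigators. That restriction is not formal masking, but it is enough to rule out asserting bias through block choice. This part of the objection stands, and no VAS bias is claimed here.

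**Participants have no reason to leave differently by arm.** They do not know their arm, and before injection their treatment does not differ. Section 13.6 is written as self-withdrawal. Early loss should therefore mainly cost precision. This stands too, except for any exit influenced by the unmasked investigator.

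**Dropout is already foreseen.** Sections 11.1 and 11.2 allow further enrollment, up to 50 per group, to account for dropouts, and 11.5 considers losing 5 per group. That covers much of the loss of precision in step 3. It does not restore equal arms, because a spent number is not reissued, and it supplies no rule for patients assigned but not injected. Pairwise deletion simply drops them from the VAS comparison.

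**Later assignment does not conceal the arm.** Under alternation, whoever knows the last number knows the next arm, and a post-operative eligibility check by that person could itself become selective. This is correct and limits what the change in timing can do alone.

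**Conclusion.** The point holds as a cheap improvement. On the preferred consent route, the plan places cancellations, withdrawals, block choice and surgery after assignment with no need to do so. Equal numbers among those injected are not assured, and block is not the pre-assignment covariate that 11.1 takes it to be.

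The consequence is mainly lost precision and balance, with a possible bias through the unmasked investigator. It is an exposure, not a demonstrated bias, and its size cannot be derived from the documents. The power figures rest on an assumed loss of 2 to 5 patients in 30 and on the plan's own difference and SD; the block figures rest on an assumed split.

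The timing is separate from the choice of sequence: a concealed random list opened at consent would leave the same interval. Equally, a later alternating assignment would leave the arm predictable.

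**What to change.** 1. At consent, issue a neutral screening ID with no arm suffix.
2. After the TKA, record the block and confirm continued participation against criteria fixed in advance.
3. Then issue the study number and arm immediately before syringe preparation, strictly in order of completed surgery. Patients lost earlier take no number and belong to no arm.
4. For the full benefit, replace alternation with a concealed random sequence opened at that moment, in permuted blocks so that the arms stay close in size. Without it, later assignment secures the group counts and keeps pre-injection losses out of the arms, but does not conceal the arm.
5. Reconcile 10.1 (Steps 1 and 2), 13.1 and 13.4 on whether consent may be taken on the day of surgery.

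The cost is a wording change to Step 2 and the ID rule, plus preparation of the concealed list for item 4. The principal investigator already draws up the syringes and goes straight to the patient (18.2), so no visit is added and the sample size does not change. The small downside is that syringes cannot be planned in advance. Patients lost before injection must still be replaced by consenting others if the target number injected is to be reached.
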